4 STUDY ENDPOINTS

4.1 Primary Efficacy Endpoint

The primary efficacy endpoint is the proportion of subjects among BoNT/A-DP and placebo groups with a FWS score of 0 or 1 and an improvement of ≥ 2 points in FWS score (at maximum frown) at the week 4 visit (of the first treatment cycle) relative to baseline (responders), based on both the investigators' and the subjects' in-clinic assessments. Thus, the primary endpoint is a composite endpoint comprising investigator and subject assessments of treatment effectiveness.

4.2 Key Secondary Efficacy Endpoint

The key secondary efficacy endpoint of this study is:

1. The extent of change in psychological impact (emotional and social functioning and concerns relating to their glabellar lines) at week 4 after the first treatment, in the BoNT/A-DP group in comparison with placebo, relative to baseline, as assessed by the modified Skindex-16 (Glabellar Line Quality of Life Scale [GL-QoL]) and the FACE-Q (Appraisal of Lines Between Eyebrows and Age Appraisal visual analog scales (VAS)), respectively.

4.3 Additional Secondary Efficacy Endpoints

The additional secondary efficacy endpoints of this study are:

2. The percentage of responders at maximum frown (as defined in 4.1 above) at week 12 (after the first treatment with BoNT/A-DP or placebo).
3. The percentage of responders at week 16 (after the first treatment).
4. The percentage of responders at week 20 or later (after the first treatment).
5. The proportion of subjects with a ≥ 1 point reduction in FWS score at rest at week 4 in the first treatment cycle, based separately on the investigators' and the subjects' in-clinic assessments (applicable only for subjects who have a FWS score at rest ≥ 1 at baseline).
6. The proportion of responders among BoNT/A-DP and placebo groups with a FWS score at maximum frown of 0 or 1 and an improvement of ≥ 2 points in FWS score (at maximum frown) during the first treatment cycle visit relative to baseline, based on both the investigators' and the subjects' in-clinic assessments (composite endpoint, at weeks 1, 2 and 8).
7. The proportion of subjects with ≥ 2 point and ≥ 1 point reduction in FWS score (at maximum frown) in the BoNT/A-DP and placebo groups during the first treatment cycle

Statistical Analysis Plan (SAP)

CROMA
est. 1976

visit relative to baseline, based on the independent rater's assessment of photographs (at baseline and visits 2, 4, 12, 16 and 20 weeks after treatment, within the first treatment cycle).

8. Time to onset of effect in the BoNT/A-DP and placebo groups in the first treatment cycle, as measured at weeks 1, 2 and 4 based separately on subject and investigator assessments. Onset of effect defined as at least a 1 point improvement in FWS score from baseline (at maximum frown). In addition, onset of effect will be assessed by subjects daily in the first 2 weeks after treatment, by recordings in the subject diary.
9. The extent of subject perceptions of effect of, and satisfaction with, treatment, in the BoNT/A-DP and placebo groups, during each treatment cycle, as assessed by the FACE-Q Satisfaction with Outcome Scale.
10. The proportion of subjects with a ≥ 1 point reduction in FWS score at rest in the BoNT/A-DP and placebo groups, relative to baseline, during the first treatment cycle, based on the independent rater's assessment of photographs.
11. The percentage of subjects with a FWS score of 0 or 1 and an improvement of ≥ 2 points in FWS score at maximum frown (investigator and subject assessment) at four weeks after re-treatment relative to the rating at the preceding end of cycle visit.
12. The proportion of subjects with ≥ 1 point reduction in FWS score (at maximum frown) in the BoNT/A-DP and placebo groups during the first treatment cycle at weeks 1, 2, 4, 8, 12, 16 and 20 relative to baseline, based on both the investigators' and the subjects' in-clinic assessments.
13. The proportion of subjects with ≥ 1 point reduction in FWS score (at maximum frown) in the BoNT/A-DP group during each re-treatment cycle at week 4 relative to re-treatment-baseline, based on both the investigators' and the subjects' in-clinic assessments.

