7. SUBJECT SELECTION, WITHDRAWAL AND DISCONTINUATION

7.1 Inclusion Criteria

Subjects who meet **ALL** of the following criteria are eligible for this study:

- Aged ≥ 18 years or older at time of screening (upper limit 75 years, inclusive).
- Has moderate to severe glabellar frown lines at maximum frown (severity score of 2 or 3 on FWS) as determined by in-clinic assessments by both the investigator and the subject (where: 0= 'none', 1= 'mild', 2= 'moderate', 3= 'severe').
- Subject has a stable medical condition with no uncontrolled systemic disease.
- Female subjects of childbearing potential must test negative for pregnancy and agree to use highly effective birth control during the course of the study.
- Subjects who wear glasses must be able to adequately self-assess the severity of their glabellar lines (according to the FWS), without glasses obstructing the forehead area.
- The moderate to severe glabellar lines have an important psychological impact on the subject as indicated by scores > 0 on either the Emotional or the Social Functioning subscale of the modified Skindex-16 (GL-QoL).

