10. ASSESSMENT OF EFFICACY

10.1 Assessment of Glabellar Line Severity: Facial Wrinkle Scale

In accordance with FDA Guidelines for Upper Facial Lines, efficacy will be determined using well defined, valid and reliable clinician-reported and subject-reported assessments, capable of measuring the critical outcomes that contribute to a conclusion of overall success or failure. For both investigator and subject assessment, measurements will be made at maximum frown (which represents the worst appearance of upper facial lines with maximum load on the muscle) and at rest (which represents the best appearance of upper facial lines with the least load on the muscle), which allows one to impute benefit when the face is in dynamic motion (variable load on the muscle).

The scale used most frequently in clinical studies is the FWS, which is a four-point rating scale as follows: 0 = no facial wrinkles; 1 = mild facial wrinkles; 2 = moderate facial wrinkles; and 3 = severe facial wrinkles. The scale has been validated and shown to be reproducible ⁴². However, this scale includes pictures at rest and at maximum frown within the one scale, meaning that the sensitivity of the scale at rest is low. The instrument proposed for use in this study is the FWS, which is named Glabellar Line Scale for Investigators [GLS-I] and Glabellar Line Scale for Subjects [GLS-S], as described in Section 20.1. The scale and the proposed instructions for its use by investigators and subjects are described in Section 20.1 and in the completion manuals: 'Glabellar Line Scale – Subject: Completion Manual', 'Glabellar Line Scale – Investigator: Completion Manual'.

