Analysis of additional secondary efficacy endpoint 4: The proportion of subjects with a ≥ 1 point reduction in FWS score at rest at week 4 in the first treatment cycle, based separately on the investigator and the subject in-clinic assessments

In general, the same statistical analyses, inclusive of the additional exploratory analyses as described for the primary efficacy endpoint, will be conducted. However, a sensitivity analysis using a tipping point analysis will not be performed.

All analyses (inclusive the additional exploratory analyses) on the investigators' in-clinic assessment will be conducted only for subjects who have an investigators' in-clinic assessment of a FWS score at rest ≥ 1 at baseline. This will similarly be applied for the analyses of the subjects' in-clinic assessment.

For the primary analysis, subjects with missing investigator in-clinic assessments of FWS score at rest at baseline or week 4 visit will be assigned as being non-responders for this efficacy endpoint. This will similarly be applied for the subjects' in-clinic assessment within the primary analysis.

As a consequence, the primary analysis of this endpoint will lead to exactly the same results as the LOCF analysis (as a subject with missing week 4 is considered as a non-responder) and thus the LOCF analysis will be skipped.

Analyses of other visits after first treatment but before re-treatment up to week 48 are exploratory only based on the FAS population using descriptive statistics only. Subjects with re-treatment before the respective visit will be excluded from the analysis. Additional exploratory analyses, as described for the primary efficacy endpoint, will not be conducted, with the exception of the calculation of 95% CIs.

Other additional secondary endpoint analyses:

Other additional secondary efficacy endpoints will be analyzed applying the appropriate statistical method for the comparison of both treatment arms. For proportions

Statistical Analysis Plan (SAP)

CROMA
est. 1976

- of responders with a FWS score of 0 or 1 and an improvement ≥ 2 points in FWS score at maximum frown (composite endpoint, at weeks 1, 2 and 8),
- of subjects with ≥ 2 and ≥ 1 point reduction in FWS at maximum frown (at baseline and visits 2, 4, 12, 16 and 20 weeks after treatment, within the first treatment cycle),
- of subjects with a ≥ 1 point reduction in FWS at rest, relative to baseline

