9 CHANGES TO PLANNED ANALYSIS FROM STUDY PROTOCOL

For the following additional secondary efficacy endpoints based on the independent rater's assessment of photographs, a worst case scenario as well as using the median value will be considered in the analyses:

- The proportion of subjects with ≥ 2 point and ≥ 1 point reduction in FWS score (at maximum frown) in the BoNT/A-DP and placebo groups during the first treatment cycle visit relative to baseline, based on the independent rater's assessment of photographs (at baseline and visits 2, 4, 12, 16 and 20 weeks after treatment, within the first treatment cycle).
- The proportion of subjects with a ≥ 1 point reduction in FWS score at rest in the BoNT/A-DP and placebo groups, relative to baseline, during the first treatment cycle, based on the independent rater's assessment of photographs.

The proportion of subjects with ≥ 1 point reduction in FWS score (at maximum frown) in the BoNT/A-DP and placebo groups during the first treatment cycle after week 20 relative to baseline, based on both the investigators' and the subjects' in-clinic assessments, will be assessed for the FAS population only. Subgroup analyses are not planned for this endpoint.

Subgroup analyses by geographic region will not be performed as this study is only being conducted in 2 countries, i.e., Austria and the US.

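### The photo-rated at-rest endpoint (item 10) is not limited to subjects who can improve at rest, so both arm rates and their difference shrink by the share scored 0 at baseline

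*SAP*

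**What the plan says.** Eligibility is set at maximum frown: "Has moderate to severe glabellar frown lines at maximum frown (severity score of 2 or 3 on FWS"), agreed by investigator and subject (Protocol 7.1). No criterion concerns the face at rest. The scale runs from 0 (none) to 3 (severe).

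Two additional secondary endpoints use the same at-rest change.

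- **Item 5**, in-clinic, week 4, analysed separately for investigator and subject. SAP 4.3 makes it "applicable only for subjects who have a FWS score at rest ≥ 1 at baseline". SAP 8.6.4 repeats the limit for each rater, requiring an "in-clinic assessment of a FWS score at rest ≥ 1 at baseline", and extends it to all the exploratory analyses of that endpoint.
- **Item 10**, the share of subjects with at least a 1-point reduction in "FWS score at rest in the BoNT/A-DP and placebo groups, relative to baseline, during the first treatment cycle, based on the independent" rater's reading of photographs. No baseline limit is attached here, in Protocol 6.4.2.2 item 10, or in the matching synopsis item.

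The list of other secondary analyses in SAP 8.6.4 has the bullet "of subjects with a ≥ 1 point reduction in FWS at rest, relative to baseline", again without a limit. SAP section 9 does revise the photo endpoints, but only in how raters are combined: "a worst case scenario as well as using the median value will be considered in the analyses". The FAS, MFAS and PP definitions do not refer to rest scores. SAP 8.6.1.1 classes all additional secondary endpoints as exploratory.

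**The concern.** A subject rated 0 at rest on the baseline photograph stays in the denominator of item 10 and can never enter the numerator. The reported rate therefore mixes two things: how often resting lines improve when there are lines to improve, and how many subjects had none. The plan separates these for item 5 and, without explanation, does not for item 10.

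What is at stake is the reading of the table. Under Protocol 10.1.2 the photographs are scored by independent blinded raters, so item 10 is the at-rest rating made by neither the subject nor the site investigator. A rate lowered by an unreported share of subjects at the floor understates the effect in those who could show one, and the reader cannot correct for it unless that share is tabulated.

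Timing matters too. SAP 8.9 does not list the photo endpoints among the interim outputs, and treatment is unblinded for that analysis. A denominator settled later would be settled with treatment codes known.

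**Working it through.** **The plan's own figure.** None: the documents give no rate, sample size or power for item 10.

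**Inputs from the documents**
- 353 subjects (SAP 5), 3:1 allocation (SAP 3.2.1): 353 × 3/4 ≈ 265 active, 353 × 1/4 ≈ 88 placebo.
- One-sided α = 0.025 for additional secondary analyses (SAP 8.6.4).

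**Inputs assumed, because the documents do not give them**
- z, the share rated 0 at rest on the baseline photograph: 10% to 50%.
- Response rates among subjects able to improve: 50% versus 10% (large effect) and 30% versus 15% (modest effect).
- z is equal in the two arms, which randomisation gives in expectation.

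**Step 1: the identity.** Subjects at the floor contribute a response rate of 0, so in each arm

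rate over all subjects = (1 - z) × rate among those able to improve + z × 0 = (1 - z) × rate among those able to improve.

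The factor is the same in both arms. The difference is multiplied by (1 - z). The rate ratio is unchanged because the factor cancels. Under the null the two diluted rates are still equal, so type I error is not inflated.

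**Step 2: size, at 50% versus 10%**

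| z | Active, all subjects | Placebo, all subjects | Difference | Rate ratio |
|---|---|---|---|---|
| 0% | 50% | 10% | 40 points | 5.0 |
| 10% | 0.9 × 50 = 45% | 0.9 × 10 = 9% | 36 points | 5.0 |
| 30% | 0.7 × 50 = 35% | 0.7 × 10 = 7% | 28 points | 5.0 |
| 50% | 0.5 × 50 = 25% | 0.5 × 10 = 5% | 20 points | 5.0 |

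Read the other way, restricting the denominator raises each rate by 1/(1 - z): 1.11, 1.43 and 2.0.

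**Step 3: power.** Normal approximation for two proportions, pooled variance under the null, one-sided 0.025. The all-subject analysis uses 265 versus 88 with diluted rates. The restricted analysis uses both arm sizes times (1 - z), rounded, with undiluted rates.

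| Rates among those able to improve | z | All subjects | Restricted |
|---|---|---|---|
| 50% v 10% | 50% | 99.8% | above 99.9% |
| 30% v 15% | 10% | 76% | 78% |
| 30% v 15% | 30% | 61% | 66% |
| 30% v 15% | 50% | 43% | 50% |

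With a large effect the floor costs essentially no power. With a modest effect it costs 1 to 7 points over this range of z.

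**The case against.** **The plan is silent on the denominator; it does not state a wrong one.** The SAP says its table templates are in a separate document, and a filter could sit there. That is fair, and the all-subject denominator is a reading of the text. It is the natural reading, since item 5 states its limit in both the endpoint list and the analysis section while item 10 has none in any of the places that define or revise it. If the limit is intended, the SAP should still say so.

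**A proportion of all randomised subjects is a legitimate quantity and matches the FAS principle.** Also fair, and the reason to keep that table. But the plan has already chosen the other denominator for the same change at rest. A baseline score is fixed before treatment, so restricting on it keeps the randomised comparison intact.

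**No inference is damaged.** This stands. A reader might infer that floor subjects tilt the test towards active or threaten a confirmatory claim. They do neither: dilution is equal across arms in expectation, and the endpoint is exploratory and outside the test hierarchy.

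**Matching denominators would not make the two at-rest rates comparable.** This stands too. A reader might infer that the denominator alone separates items 5 and 10. Item 5 is a week 4 in-clinic score, reported per rater. Item 10 comes from photographs, which are rated at baseline, week 2, week 4 and the visit preceding re-treatment (Protocol 10.1.2), and is summarised by worst case and by median. The documents plan no comparison of the two. The restriction removes one cause of difference among several.

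**The remark on low sensitivity at rest.** A reader might take "meaning that the sensitivity of the scale at rest is low" (Protocol 10.1) as evidence that many subjects score 0. The sentence concerns a scale that places rest and frown pictures together, and it says nothing about how scores are distributed. This point does not rest on it.

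**Conclusion.** The concern holds in a limited form. As written, item 10 keeps in its denominator subjects who cannot respond, while the plan removes such subjects from the in-clinic endpoint that uses the same change. Rates and difference are multiplied by (1 - z).

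The direction and the form of the shrinkage follow from the scale and the definition. The size does not: z and the underlying rates are assumptions. At z = 10% a 40-point difference becomes 36, which matters little. At z = 50% it becomes 20, which would change how the table reads. The identity also assumes that subjects have a readable baseline photograph. The text for item 10 gives no rule for missing ones.

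This is a worthwhile improvement to an exploratory table. It does not affect the primary or key secondary results.

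**What to change.** In SAP 4.3 item 10, SAP 8.6.4 and SAP section 9, and in Protocol 6.4.2.2 item 10 (with the matching synopsis item):

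1. State that the main analysis of item 10 includes only subjects with an independent-rater rest score of at least 1 on the baseline photograph.
2. Fix one rater rule for that baseline score, for example the median, before unblinding, and use it for both the median and the worst-case tables. If each table used its own rule, they could have different denominators. The SAP should also define what worst case means, which it does not do now.
3. Report the number scored 0 at baseline in each arm.
4. Keep the all-subject table as supportive.

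**Cost.** No new data: the baseline photographs are already scored. The work is a short SAP edit, one filter and one count. The denominator is smaller and the interval wider. For example, at z = 30% and 50% response among those able to improve, the normal-approximation 95% half-width in the active arm is 1.96 × √(0.35 × 0.65 / 265) = 5.7 points for all subjects and 1.96 × √(0.50 × 0.50 / 186) = 7.2 points for the restricted set (265 × 0.7 ≈ 186).

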If at an Evaluation for Re-treatment visit the subject wants to get re-treated, but the investigator does not agree or vice versa (i.e., the FWS score is not \geq at least 2 by both assessments), the subject will return to the site four weeks thereafter for another Evaluation for Re-treatment visit. There is no limit to the number of Evaluation for Re-treatment visits. In order to consider a visit as the End of Cycle visit, there must always be agreement between investigator and subject on a FWS score (at maximum frown) of ≥ 2 .

End of Study Visit

The End of Study visit can take place in four-weekly intervals from study-week 48 until study-week 60. The last study drug re-treatment will be administered no later than week 48. For subjects receiving a re-treatment at week 48, the last cycle will end 12 weeks later at week 60 (i.e., End of Study visit).

The End of Study visit will take place at week 48 if the week 48 visit is an Evaluation for Re-treatment visit and the subject does not meet the criteria for re-treatment in case this visit is 12 or more weeks after the last treatment. As week 48 is the last possible time point for re-treatment, such subjects will continue with all additional assessments of the End of Study visit on the same day. For subjects having received their last injection eight weeks or less prior to week 48, the End of Study visit will take place 12 weeks after the last study drug treatment was given, e.g. week 52 if the subject was re-treated at week 40.

For subjects who are prematurely discontinued from the study (at any time), the End of Study visit will take place within one week of discontinuation.

A detailed description of procedures and assessments to be conducted during this study is summarized in the Scheduled of Study Assessments in Table 1 below.

COVID-19 Pandemic

Due to the COVID-19 pandemic, which touched the world mainly the first 6 months of 2020, it has been allowed that visits were done remotely instead of physically when site was closed.

All re-treatments were put on hold between the 16th March and 5th May 2020 due to concerns that the subject will not be able to return for Week 1 and Week 4 assessments. Consequently, when a subject was eligible for re-treatment at a visit, the injection has been delayed until the subject could go back to site (if the injection is done before or at Week 48).

	Statistical Analysis Plan (SAP)	croma est. 1976
---	--	---------------------------

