*** Full physical examination will include neurological assessment (including extraocular movements and cranial nerves) as well as assessment for muscle weakness. In addition, if the subject reports any symptoms related to Adverse Events of Special Interest (as detailed in the AESI Manual) a focused physical examination, to evaluate these symptoms will also be undertaken.

§ The ECG performed at screening is the baseline ECG. Laboratory and Anti-drug-antibody (ADA) test samples from screening are considered baseline values.

1 Depending on the duration of treatment effect, a maximum of 4 treatments is permitted.

2 Evaluation for re-treatment takes place at the earliest at 12 weeks after the first/previous treatment. Subjects who do not qualify for re-treatment at week 12 will have the option (pending eligibility) for re-treatment at 4-weekly intervals thereafter, until they are eligible for re-treatment. Once the subject is eligible for re-treatment, the end of cycle procedures will take place and the subject can receive re-treatment (i.e. the end of cycle visit and the re-treatment visit will be conducted on the same day as the Evaluation for Re-treatment visit).

3 The latest time for re-treatment is study week 48; if a subject is not eligible for re-treatment at study week 48, the End of Study visit will be completed.

4 The End of Study visit can take place in four-weekly intervals from study-week 48 until study-week 60. For subjects receiving re-treatment at week 48, the last cycle will end 12 weeks later at week 60 (=End of Study visit). End of Study visit will take place at week 48 if week 48 visit is an Evaluation for Re-treatment visit and the subject is not meeting the criteria for re-treatment. For subjects having received their last injection 8 weeks or less prior to week 48, the End of Study visit will take place 12 weeks after the last study drug treatment was given, e.g. week 52 if subject was retreated at week 40. For subjects that get prematurely discontinued from the study (at any time) the End of Study visit will take place within 1 week of discontinuation.

5 Only in women of child-bearing potential; blood serum test at screening and End of Study visit; otherwise urine dip stick.

6 Vital signs include blood pressure (diastolic /systolic) and pulse.

7 Laboratory Assessments: Hematology and Serum Chemistry, details in Section 11.15 of the study protocol..

Statistical Analysis Plan (SAP)

croma
est. 1976

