8.5 Extent of Exposure

8.5.1 Duration of Study Drug Exposure

Duration of study drug exposure (in days) will be calculated as date of last study medication exposure minus date of first study medication administration + 1 day, regardless of study drug interruption. Details of study drug exposure derivation is described in Section 7.1.

Study drug exposure will be summarised by treatment group and separated for the double blind and open label phase on the SAF population using time intervals and summary statistics. Planned and actual dose as well as injections at all sites per subject and treatment cycle will be listed.

Due to the COVID-19 pandemic and the treatment hold, the duration of study drug exposure will be also derived as described above but excluding the days between the end of cycle visit and the re-treatment visit between each cycle. This will be summarized using summary statistics.

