8.7 Safety Analyses

This section describes the safety analyses that will be conducted on the double blind and the open label treatment period, i.e., the safety analyses on all data collected during these treatment periods and all data collected in subjects who dropped-out during one of the treatment periods.

All definitions relative to safety endpoints are detailed in the following sections.

Safety analyses will be conducted on the SAF population and will be performed for all safety variables specified below.

All safety data will be summarized by treatment group.

The safety analyses of changes from baseline to a specific time point in safety variables (e.g., laboratory parameters, vital signs, and ECG) will only include subjects from the SAF population who have data available for both the baseline and the time point under consideration unless otherwise specified.

No statistical testing methods will be applied to statistically evaluate the differences on safety variables between treatment groups. Safety endpoint variables will be analyzed descriptively only.

An additional safety evaluation will be performed for laboratory data, vital signs, and ECG by defining cycle 2 day 0 as baseline (or last available value before drug administration of Cycle 2) for all subjects.

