- The proportion of subjects with ≥ 1 point reduction in FWS score (at maximum frown) in the BoNT/A-DP and placebo groups during the first treatment cycle at week 12, 16 and 20 relative to baseline, based on both the investigators' and the subjects' in-clinic assessments: by site, by country and by subjects with previous use of botulinum toxin versus naïve subjects.

Subgroup analyses will be performed on the FAS, MFAS and PP populations.

COVID-19 Pandemic:

Due to COVID-19 pandemic, the secondary endpoints 'the percentage of subjects with an improvement of ≥ 2 points in FWS at maximum frown at 4 weeks after re-treatment' and 'the percentage of subjects with ≥ 1 point reduction in FWS score at maximum frown at week 4 relative to re-treatment baseline' will be also analyzed using observed values by the FWS investigator assessment type (i.e. assessment done remotely or physically). The objective is to assess if the remote way has not impacted the investigator assessment.

These analyses will be performed for the final analysis.

Exclusion of Site 110 Subjects:

A site audit conducted in January 2019 as pointed out a critical finding on a protocol non-compliance: an unblinded site staff performed blinded tasks on safety assessments. In order to assess the impact on the results, analyses based on FAS for primary and secondary efficacy endpoints relative to the double-blind period of the trial will be repeated excluding all the subjects of the site 110.

AE summary tables for TEAEs and AESIs, and TEAEs and AESIs summarized by SOC, PT will be also repeated for each site and by excluding all the subjects of the site 110.

These analyses will be performed for the interim and final analyses.

Statistical Analysis Plan (SAP)

CROMA
est. 1976

ADA, laboratory, vital signs and ECG analyses will be also repeated by excluding all the subjects of the site 110 only for the final analysis.

Further analyses may be performed to assess the site 110 effect, if needed.

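### Endpoint 11 scores re-treatment response against the End of Cycle FWS; the COVID-19 hold could put that rating seven weeks or more before the injection, and no planned efficacy analysis looks at the delay

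*SAP*

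**What the plan says.** **Reference rating.** SAP 4.3 measures endpoint 11 "relative to the rating at the preceding end of cycle visit"; Protocol 6.4.2.2 and 10.1.1 define it the same way. The missing-data rule in SAP 7.2.1 and the McNemar comparison in SAP 8.6.4 rely on that same visit. Endpoint 13 is worded differently, "at week 4 relative to re-treatment-baseline", and neither document says which rating that is.

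**Timing by design.** SAP Table 1, footnote 2, provides that "the end of cycle visit and the re-treatment visit will be conducted on the same day as the Evaluation for Re-treatment visit". Protocol 2.1 and 6.3.2 agree. The schedule in Protocol 2.1 places the FWS at the Evaluation for Re-treatment visit and shows none in the Re-treatment column.

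**What happened.** SAP 3.3 states: "All re-treatments were put on hold between the 16th March and 5th May 2020". For a subject who was eligible in that period, "the injection has been delayed until the subject could go back to site", provided this was no later than week 48.

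**What the SAP did about it.** SAP 8.5.1 adds a second exposure duration, "excluding the days between the end of cycle visit and the re-treatment visit between each cycle". SAP 8.8.1 adds an analysis of the two re-treatment endpoints by whether the investigator's FWS was remote or physical: "The objective is to assess if the remote way has not impacted the investigator assessment". No efficacy analysis uses the length of the delay.

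**The concern.** The End of Cycle rating can stand in for the score at injection because no time is meant to pass between them. In cycles caught by the hold, weeks could pass, and the effect of the previous injection may have gone on fading. The week-4 rating is then compared with a score that may no longer have applied when the subject was injected.

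Efficacy after repeat treatment is part of the stated purpose of the study (Protocol 5.1). If held cycles are scored against an older reference than unheld cycles, response rates can differ between cycles for reasons unrelated to the product, and no planned table would show it. The remote-versus-physical split concerns how a rating was made, not how old the reference was.

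**Working it through.** The SAP states no gap length, so there is no figure of its own to reproduce. The check has three parts.

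**1. Length of the hold** (dates from SAP 3.3). 16 to 31 March is 15 days, April is 30, and 1 to 5 May is 5: 15 + 30 + 5 = 50 days, and 50 / 7 = 7.1 weeks (51 days, 7.3 weeks, counting both end dates). Against the 12-week minimum cycle, 50 / 84 = 60%. A subject found eligible on the first day and injected when the hold was lifted has a gap of about 7.1 weeks. It is longer if the return to site came after 5 May and shorter if eligibility came later in the hold.

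**2. Which results change.** An End of Cycle visit requires FWS of at least 2 from both raters (SAP 3.3), so the reference is 2 or 3. Endpoint 11 needs a week-4 score of 0 or 1 and a drop of at least 2 points; endpoint 13 needs a drop of at least 1 point. If the score is the same at End of Cycle and at injection, the choice of reference makes no difference. If it rose from 2 to 3:

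| Week-4 score | Endpoint 11, from End of Cycle (2) | Endpoint 11, from injection (3) | Endpoint 13, from End of Cycle (2) | Endpoint 13, from injection (3) |
|---|---|---|---|---|
| 0 | yes | yes | yes | yes |
| 1 | **no** (2 - 1 = 1) | **yes** (3 - 1 = 2) | yes | yes |
| 2 | no | no | **no** (2 - 2 = 0) | **yes** (3 - 2 = 1) |
| 3 | no | no | no | no |

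One cell changes per endpoint. The endpoint 13 columns apply only if re-treatment-baseline is read as the End of Cycle rating. Both raters must meet the criterion, so one rater's outdated 2 is enough to turn a response into a non-response. For the result to reverse, every rater who fails against an End of Cycle score of 2 must have moved to 3.

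A fall from 3 to 2 before injection acts the other way. With a week-4 score of 1, endpoint 11 is met from End of Cycle (3 - 1 = 2) and not from injection (2 - 1 = 1).

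**3. Possible size.** The understatement of the endpoint 11 rate in a cycle is f x g x h, where f is the share of the cycle delayed, g the share of those moving from 2 to 3, and h the share of those scoring 1 at week 4, treating the two raters as moving together. None of the three is in the documents. With assumed ranges f = 10-50%, g = 5-20% and h = 30-50%:

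- low: 0.10 x 0.05 x 0.30 = 0.0015, or 0.15 percentage points
- high: 0.50 x 0.20 x 0.50 = 0.05, or 5 percentage points

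This shows only how the parts combine. It is not an estimate for this trial.

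**The case against.** Several points on the other side hold.

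- **Low consequence.** SAP 8.6.1.1 makes all additional secondary endpoints exploratory. These are open-label and uncontrolled, and the responder analysis leaves out subjects who started on placebo (SAP 8.6.4). The primary and key secondary endpoints are taken at week 4 of cycle 1 and do not use this reference. A downward bias cannot create an efficacy claim.
- **A subset only.** A subject already at 3 at End of Cycle cannot go higher, and one who entered at 2 and is back at 2 has returned to the entry score. A rise from 2 to 3 chiefly concerns subjects who entered at 3 and had relapsed only to 2.
- **Redefining the baseline may change nothing.** No FWS is scheduled at the Re-treatment visit. If none was repeated at the delayed injection, the last rating before injection is still the End of Cycle one. SAP 3.3 refers to CRF completion guidelines, which are not available here and might cover this. Changing endpoint 11 itself would also depart from the protocol definition during the study.

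It could also be argued that the End of Cycle visit simply moved to the injection date. SAP 8.5.1 speaks against that: there would then be no days between the two visits to exclude.

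A reader might infer three stronger things that the documents do not support:

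- That both endpoints are tied to End of Cycle. Only endpoint 11 is. The general baseline definitions (SAP 7.1 and 8.1, Protocol 12.5.1) refer to the first treatment and do not settle endpoint 13.
- That the SAP corrected this for safety data and overlooked FWS. The fallback in SAP 8.7, "or last available value before drug administration of Cycle 2", does not mention COVID-19 and covers Cycle 2 only. Protocol 12.4.2 had already planned a cycle 2 baseline for subjects switching from placebo.
- That the remote/physical split covers only the week-4 rating. SAP 8.8.1 does not say which rating it uses.

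**Conclusion.** The point stands in a limited form. For endpoint 11, a stated rule gives an outdated reference in any cycle where the hold separated the End of Cycle visit from the injection. The SAP recognises that gap for exposure but makes no provision for it in efficacy. For endpoint 13 the defect is an undefined term, and the same problem follows only under one reading of it.

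The bias is probably downward, on the assumption that untreated lines stay the same or worsen; rater variation could offset it. Its size is unknown because the documents give neither the number of delayed subjects nor the gap lengths. A reader might be tempted to treat every subject whose score rose while waiting as misclassified. That overstates it, since only those with one particular week-4 score change class. This is a cheap improvement to exploratory analyses and no threat to the trial's confirmatory conclusions.

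**What to change.** - Keep the protocol definition of endpoint 11 as the main analysis.
- In SAP 8.8.1, add a final-analysis sensitivity table for endpoints 11 and 13 that excludes, or shows separately, cycles in which the injection was not on the End of Cycle date. A threshold of more than 5 days, the general visit window in Protocol 6.3.5, is an alternative.
- Where a repeat FWS by both raters was recorded on or before a delayed injection, also use it as the reference in that sensitivity analysis, and state how many cycles have one.
- Define re-treatment-baseline for endpoint 13 as the last FWS by both raters on or before the injection.

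The cost is a few lines of SAP text and one extra table. Separating the cycles needs only the visit and injection dates that SAP 8.5.1 already uses. The downside is a smaller n in the sensitivity set.
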